Number of Study Centers	Multicenter
Clinical Phase	III
Investigational Agent	APR-246
Study Design	
This study will be a multi-center, open-label, randomized, controlled Phase III trial to compare the efficacy of APR-246 in combination with azacitidine versus azacitidine alone for the treatment of TP53 mutant myelodysplastic syndromes.
 
Patients will be randomized (1:1) to one of two treatment arms and stratified by age (< 65 versus ≥ 65):
 
 1) Experimental arm: APR-246 + azacitidine; or 2) Control arm: Azacitidine 
The Intent-to-Treat (ITT) population will be the primary analysis population for efficacy. All patients who are randomized on study will be considered eligible for the ITT population and will be used for demographics, baseline characteristics summaries.
 
Patients may continue treatment as long as toxicity remains acceptable, progression has not occurred and the patient has not withdrawn consent. Response and progressive disease will be assessed based on the Guidelines for Implementation of International Working Group (IWG) response criteria after every two treatment cycles the first year, then every three cycles. Patients may remain on protocol therapy after relapse or progression if they are continuing to derive clinical benefit in the opinion of the Investigator.
 
Investigators may choose to transition patients towards a stem cell transplantation (SCT) as appropriate after a response by the experimental or control treatment has been achieved. Patients who undergo SCT will be removed from study treatment and will be followed per the study calendar.

Study Objectives	
Primary Objective:
 
 1. To compare the complete response rate, defined as the proportion of patients who achieve complete remission (CR), and duration of CR with

	
APR-246 + azacitidine treatment vs. azacitidine only. Secondary Objectives: To measure the following with APR-246 + azacitidine treatment vs. azacitidine alone:
 
 1. Overall response rate (ORR) 2. Duration of response (DOR) 3. Rate and time to acute myeloid leukemia (AML) transformation 4. Overall survival (OS) 5. Relapse-free survival (RFS) 6. Transition rate to hematopoietic stem cell transplant (HSCT) 7. Safety profile 8. Rate of red blood cell (RBC) and/or platelet transfusion independence (TI) for 56 days (8 weeks) 9. Pharmacokinetics of APR-246 and azacitidine 
Exploratory Objectives:
 
 1. Determine if biomarkers predictive for response to therapy can be derived from baseline molecular analyses of bone marrow or blood samples 2. Determine the depth of remission by IHC, PCR, and other techniques in serial bone marrow or blood samples 3. Investigate potential resistance mechanisms by molecular analysis of bone marrow or blood samples at disease progression 
VAF

Study Endpoints
	
Primary Endpoint: CR per the modified IWG (Cheson et al, 2006)¹ and time between achieving CR and relapse of disease. Secondary Endpoints:
 
 1. ORR is the proportion of patients achieving hematological improvement (HI), partial remission (PR), CR, marrow CR by the IWG 2006 criteria 2. Response duration 3. AML transformation according to World Health Organization (WHO) criteria 4. OS 5. RFS 6. Proportion of patients who transition to HSCT 7. Safety endpoints can relate to adverse events, serious adverse events, dose adjustments or dose holds, lab parameter values, vital signs, ECGs 8. Patients who achieve RBC and/or platelet TI during the 56-day (8 week) period after randomization 9. Pharmacokinetic endpoints: C_{max} (maximum concentration), AUC (area under the curve), Vd and clearance (CL) of APR-246 and azacitidine 
Exploratory Endpoints:
 
 1. Baseline molecular analyses may include, but are not limited to: TP53 VAF by NGS, p53 immunohistochemistry, mutations in other genes by NGS, RNA expression 2. Investigations of depth of remission may include, but are not limited to: PCR and p53 immunohistochemistry 3. Molecular analyses at disease progression may include, but are not limited to: TP53 VAF by NGS, p53 immunohistochemistry, mutations in other genes by NGS, RNA expression

Eligibility Criteria	
Inclusion Criteria:
 
1. Patient has signed the Informed Consent (ICF) and is able to comply with protocol requirements2. Documented diagnosis of MDS, according to WHO classification (<20% blasts), that meets IPSS-R classification of intermediate, high, or very high-risk disease3. Patient has adequate organ function as defined by the following laboratory values:
a) Creatinine clearance > 30 mL/min (by Cockcroft-Gault method; see Appendix IV)b) Total serum bilirubin < 1.5 × ULN unless due to Gilbert's Syndrome, underlying disease of MDS, hemolysis or considered an effect of regular blood transfusionsc) Alanine aminotransferase (ALT) and aspartate aminotransferase (AST) < 2.5 × ULN, unless due to underlying disease of MDS4. Age ≥18 years at the time of signing the informed consent form (ICF)5. Having at least one TP53 mutation which is not benign or likely benign6. Eastern Cooperative Oncology Group (ECOG) performance status score of 0, 1, or 27. Females of childbearing potential: negative pre-treatment urine or serum pregnancy test8. Females of childbearing potential and males with female partners of childbearing potential must be willing to use an effective form of contraception such as latex condom, hormonal birth control, intrauterine device or double barrier method during chemotherapy treatment and for at least six months thereafter 
Exclusion Criteria:
 
1. Patient has a known history of HIV or active hepatitis B or active hepatitis C infection (testing not mandatory).2. Patient has any of the following cardiac abnormalities (as determined by treating MD):
a) Myocardial infarction within six months prior to registration,b) New York Heart Association Class III or IV heart failure (see Appendix III) or known left ventricular ejection fraction (LVEF) < 40%, as assessed by echocardiogram or MUGA scan;c) A history of familial long QT syndrome,d) Symptomatic atrial or ventricular arrhythmias not controlled by medications,e) QTc ≥ 470 msec calculated from a mean of 3 ECG readings using Fridericia's correction (QTcF = QT/RR^{0.33}). Note: Patients with QTcF ≥ 470 msec and with bundle branch block and/or pacemaker rhythm may be enrolled after approval by Medical Monitor.3. Concomitant malignancies or previous malignancies with less than a 1-year disease free interval at the time of signing consent. Patients with adequately resected basal or squamous cell carcinoma of the skin, or
-----------------------------	---

	
adequately resected carcinoma in situ (e.g. cervix) may enroll irrespective of the time of diagnosis.
 
 4. Prior exposure to azacitidine, decitabine or investigational hypomethylating agent or induction chemotherapy for MDS or AML. Note: intensive chemotherapy for any other prior cancer is not exclusionary. 5. Use of cytotoxic chemotherapeutic agents, or experimental agents (agents that are not commercially available) for the treatment of MDS within 14 days of the first day of study drug treatment. 6. Concurrent use of erythroid stimulating agents, G-CSF, or GM-CSF within 14 days of the first day of study drug treatment. 7. History of allogeneic stem cell transplantation 8. Pregnancy: Pregnant women are excluded from this study because APR-246 has not been studied in pregnant patients. Because there is an unknown but potential risk for adverse events in nursing infants secondary to treatment of the mother with APR-246, breastfeeding should be discontinued if the mother is treated with APR-246. 9. Active uncontrolled infection.

Treatment plan
	
Treatment will be administered on an outpatient basis. No investigational or commercial agents or therapies other than those described below may be administered with the intent to treat the patient's disease.
 
Patients will be randomized (1:1) to 1 of 2 arms and stratified by age (<65 versus ≥65):
 
 1) Experimental: APR-246 + azacitidine; or 2) Control: azacitidine only 
Treatment Schedule for Experimental Arm: APR-246 + Azacitidine
 
  
 
APR-246 will be administered as a 6-hour intravenous (IV) infusion daily on days 1-4 of each 28-day cycle. APR-246 fixed dose is 4.5 g. One dose level reduction to 4.0 g is permitted. A second dose reduction could be permitted following discussion with the Sponsor and Medical Monitor.
 
Azacitidine will be given at the standard dose of 75 mg/m² over 7 consecutive days (Days 4-10) as a subcutaneous injection or IV infusion, every 28 days.
 
Control arm: Azacitidine (75 mg/m²) only, on Days 4-10, as a subcutaneous injection or IV infusion, every 28 days.

Dose delay / modifications
	
Dose delays/modifications are permitted per protocol. A single missed dose may be compensated by adding an additional dosing day for azacitidine, so that the patient

	receives the total 7 days of treatment per cycle (see Section 6.2.1).
Duration of Treatment	The projected Phase III duration is 30–36 months. Patients may continue treatment to the end of the trial while deriving clinical benefit, unless unacceptable toxicity, progression, death or patient withdrawal requires discontinuation. Patients may remain on protocol therapy after relapse or progression if they are continuing to derive clinical benefit in the opinion of the Investigator.
Duration of Follow-Up	
Assuming there is no withdrawal of consent, patients who stop study treatment (APR-246 or azacitidine) for any reason (e.g. toxicity, transition to SCT, PD) will continue long term follow-up:
 
 1. Patients who discontinue study treatment to receive SCT: 
 a. Collect post SCT response assessments, transformation to AML and survival every month until relapse or death, whichever occurs first. b. After PD, collect data for survival and transformation to AML every 6 months until death. 2. Responders (CR, PR, mCR with HI, mCR without HI, HI) who discontinue study treatment for other reasons than progressive disease or SCT: 
 a. Collect response assessments, transformation to AML and survival every month until relapse or death, whichever occurs first. b. After relapse/progression, continue collecting data for survival and transformation to AML every 6 months until death. 3. Non-Responders: patients who discontinue study treatment due to progressive disease: 
 a. Collect data for survival and transformation to AML every 6 months until death. 
If a patient is removed from the study treatment due to unacceptable adverse events, the event(s) will be followed until resolution or stabilization.
 
Criteria for Removal from Study
 
Study drug treatment can continue for patients receiving clinical benefit, unless: one or more withdrawal criteria are met, or at the patient’s discretion, or if the study is terminated.
 
 1. Patient Completion 
A patient will be considered to have completed the study if the patient meets at least 1 of the following criteria:
 
 • The patient has progressive disease. • The patient died during the study. • The patient experienced a treatment related AE that led to withdrawal from the study. • The patient starts new treatment for their underlying disease (MDS). 
 2. Patient Withdrawal from Study Treatment: 
If the patient is permanently withdrawn from study treatment, but does not withdraw consent to be followed on study, the investigator must make every effort

	
to have the patient complete all withdrawal assessments at the time of withdrawal, and complete all scheduled follow-up visits.
 
3. Patient Withdrawal from Study:
 
A patient may voluntarily withdraw from study treatment or withdraw consent from the study at any time. The investigator may also, at his or her discretion, discontinue a patient from participating in the study at any time. The investigator and/or designated staff will record the date and the reason for patient withdrawal from the study.
 
Study treatment must be discontinued if:
 
 - Evidence of disease progression according to IWG 2006 criteria. - A patient becomes pregnant. - A patient is significantly non-compliant with the requirements of the protocol. - A patient has an adverse experience that would, in the Investigator's judgment, make continued participation in the study an unacceptable risk. - A patient withdraws consent. - A patient receives HSCT.

Follow-Up on study
	
See Schedule of Study Evaluations.


Statistics
	
This study will be a multi-center, open-label, randomized, controlled Phase III trial to compare the efficacy of APR-246 in combination with azacitidine versus azacitidine alone for the treatment of TP53 mutant MDS.
 
Analysis Populations
 
Intent-to-treat (ITT): All patients who are randomized on study will be considered eligible for the ITT population and will be used for demographics, baseline characteristics summaries. The ITT population will be the primary analysis population for efficacy.
 
Efficacy evaluable (EE): All patients who complete at least one treatment cycle of APR-246 and azacitidine and who have at least one post-treatment clinical response assessment. Patients who fail to complete one treatment cycle will also be considered EE if they show clear evidence of clinically significant disease progression. The EE population will be the secondary analysis population for efficacy.
 
Safety population: Patients will be evaluable for safety if they receive at least one dose of APR-246 or azacitidine. The safety population will be used to summarize exposure and safety parameters.
 
Pharmacokinetics (PK): Patients will be evaluable for pharmacokinetics if at least one sample for PK evaluation has been obtained.
 
Determination of Sample Size
 
This trial assumes a sample size of 154 patients with 77 patients randomized in a 1:1 ratio to one of the two treatment arms (APR-246 + azacitidine treatment versus

azacitidine treatment alone). If the true CR rate is 50% for the treatment arm and 25% for the control arm, the trial will have 90% power to detect a statistically significant effect in favor of the APR-246 treatment combination at a 2-sided alpha = 0.05 significance level.

Efficacy Analyses

Primary endpoint CR will be summarized for all randomized patients (ITT) as the proportion of patients (%) with CR. CR will be compared between arms using a Cochran-Mantel-Haenszel (CMH) test stratified by age (< 65 years versus ≥ 65 years). In addition to presenting the CR rate and associated exact 95% confidence intervals (CI) for each treatment arm, the treatment effect will be described using the CMH estimate of the common odds ratio together with its associated 95% CI.

Duration of response (DOR) is defined as the time from the date when criteria for response are met to the date of progressive disease or death due to any cause, whichever occurs first. Patients alive with no progressive disease will have their DOR censored at the date of the last clinical assessment. The duration of CR will be summarized in each treatment arm by providing the median DOR together with associated 95% (CI), using Kaplan-Meier methodology.

Overall response will be summarized in number (%) of patients in each category of responses (CR, PR, mCR with HI, mCR without HI, HI). ORR will be analyzed by using the similar method as primary endpoint CR. DOR, as defined above, will also be evaluated in regard to ORR. Time to AML is calculated from first day of study treatment to first onset of AML. Kaplan-Meier methodology will be utilized. Rate of AML transformation will be analyzed by using the similar method as primary endpoint CR.

Survival data are collected at treatment and follow-up periods. Patients will be followed until death. Overall survival (OS) is defined as the number of days from the date of randomization to the date of death. Kaplan-Meier methodology will be utilized.

Relapse-free survival (RFS) is defined as the time from the date of randomization to disease relapse or death from MDS, whichever occurs first. If neither event occurs, RFS will be censored at the date of the last clinical assessment. Kaplan-Meier methodology will be utilized.

Time to AML, OS and RFS will be analyzed using the similar methods as DOR.

Transition rate to HSCT will be analyzed using the similar methods as primary endpoint CR.

Safety Analyses

Safety data including adverse events, vital signs, laboratory data, ECG, physical exam will be tabulated for the safety population. Adverse events will be tabulated by body system, preferred term, severity, and relationship to treatments. The tabulation of laboratory parameters will include the normal ranges for each parameter. Each value will be classified as falling above, below, or within the normal range. Laboratory parameters will also be tabulated by maximum NCI-

	
CTCAE v5.0 severity grade.
 
Pharmacokinetic Analysis
 
In Experimental Arm, sparse PK sampling for APR-246 will be done at all sites in cycles 1-3, on Days 1, 2 and 4.
 
In both Arms, azacitidine PK will be performed at selected sites in cycle 1, on Day 4.
 
The pharmacokinetics of APR-246 and azacitidine will be summarized using descriptive statistics.
 
For APR-246, a population PK model will be used to estimate individual C_{max}, AUC and CL for each patient. APR-246 AUC and C_{max} will then be tested for association with signs of efficacy and safety. If an observable trend exists, a PK/PD model will be developed to evaluate the exposure-response relationship between APR-246 plasma exposure and outcome measures. Demographic and clinical data (ethnicity, current age, body weight, sex, disease status, etc.) will be utilized to assess interpatient variability in the PK and PK/PD relationships.
 
For azacitidine non-compartmental methods will be used to derive PK parameters (C_{max}, T_{max}, AUC, V and CL).

--	--

LIST OF ABBREVIATIONS

ALP	Alkaline Phosphatase
ALT	Alanine Aminotransferase
AML	Acute Myeloid Leukemia
ANC	Absolute Neutrophil Count
AST	Aspartate Aminotransferase
AUC	Area Under the Curve
CBC	Complete Blood Count
CL	Clearance
CI	Confidence Interval
CLL	Chronic Lymphocytic Leukemia
C _{max}	Maximum Concentration
CMH	Cochran-Mantel-Haenszel
CMML	Chronic Myelomonocytic Leukemia
CNS	Central Nervous System
CR	Complete Remission
CRF	Case Report Form
CRO	Contract Research Organization
CTCAE	Common Terminology Criteria for Adverse Events
DAR	Drug Accountability Record
ddPCR	Digital Droplet Polymerase Chain Reaction
DILI	Drug-Induced Liver Injury
DL	Dose Level
DLT	Dose-Limiting Toxicity
DNA	Deoxyribonucleic Acid
DNMT	DNA Methyltransferase
DOR	Duration of Response
ECG	Electrocardiogram
ECOG	Eastern Cooperative Oncology Group
EE	Efficacy Evaluable
E _{max}	Maximal Effect
EOI	End of Infusion
ESA	Erythropoietic Stimulating Agent
EU	European Union
FAB	French–American–British Classification System
GCP	Good Clinical Practices
G-CSF	Granulocyte-Colony Stimulating Factor
GLP	Good Laboratory Practices
GM-CSF	Granulocyte Macrophage-Colony Stimulating Factor
GMP	Good Manufacturing Practices
hERG	Human Ether-a-Go-Go Gene
HFD	Highest Feasible Dose

Hgb	Hemoglobin
HGSOC	High Grade Serous Ovarian Cancer
HMA	Hypomethylating Agent
HI	Hematologic Improvement
HIV	Human Immunodeficiency Virus
HPLC	High Performance Liquid Chromatography
HR	Hazard Ratio
HSCT	Hematopoietic Stem Cell Transplant
IB	Investigator's Brochure
IEC/IRB	Independent Ethics Committee/Institutional Review Board
ICF	Informed Consent Form
IM	Intramuscular
IMP	Investigational Medicinal Product
IPSS/IPSS-R	International Prognostic Scoring System/ Revised IPSS
ITT	Intent-to-Treat
IV	Intravenous
IWG	International Working Group
IWRS	Interactive Web Response System
LBM	Lean Body Mass
LFT	Liver Function Test
LVEF	Left Ventricular Ejection Fraction
mCR	Marrow Complete Remission
MDS	Myelodysplastic Syndrome
MedDRA	Medical Dictionary for Regulatory Activities
MM	Multiple Myeloma
MQ	2-Methylene-Quinuclidin-3-One
MTD	Maximum Tolerated Dose
NCI-CTCAE	National Cancer Institute – Common Terminology Criteria for Adverse Events
NGS	Next Generation Sequencing
NHL	Non-Hodgkin's Lymphoma
NOAEL	No Observed Adverse Effect Level
ORR	Overall Response Rate
OS	Overall Survival
PD	Progressive Disease
PHL	Potential Hy's Law
PI	Principal Investigator
PK	Pharmacokinetics
PLD	Pegylated Liposomal Doxorubicin
PR	Partial Remission
RA	Refractory Anemia
RAEB	Refractory Anemia with Excess Blasts
RAEB-T	Refractory Anemia with Excess Blasts in Transformation

RBC	Red Blood Cell
RFS	Relapse-Free Survival
ROS	Reactive Oxygen Species
SAE	Serious Adverse Event
SC	Subcutaneous
SCT	Stem Cell Transplant
TEAE	Treatment Emergent Adverse Event
TI	Transfusion Independence
TID	Three Times a Day (Ter in Die)
T _{max}	Time of Maximum Concentration
TrxR1	Thioredoxin Reductase
ULN	Upper Limit Normal
US	United States
VAF	Variant Allele Frequency
V _d	Volume of Distribution
WHO	World Health Organization

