6.1.1 Experimental Arm (APR-246 + Azacitidine)

APR-246 will be administered as a 6-hour intravenous infusion daily on days 1-4 of each 28-day cycle. APR-246 fixed dose is 4.5 g. APR-246 is administered in a 2-step infusion:

Step 1: Loading dose of 1.5 g for the first 45 minutes (± 2 min)

Step 2: Maintenance dose of 3 g over 5 hours 15 minutes (± 30 min)

Detailed instructions on vial concentration, preparation and dispensing can be found in the Pharmacy Binder. The infusion timing, including start/stop times and the time of rate change, must be recorded.

Azacitidine will be given at the standard dose of 75 mg/m² SC or IV over 7 consecutive days, Days **4-10**. On **Day 4** azacitidine is administered immediately after the APR-246 infusion. SC method is preferred but IV is allowed at the Investigator's discretion. However, the same route should be maintained over the 7-day treatment period (whichever route is used on Day **4**, the other days should follow the same route of administration). Detailed instructions on preparation and administration can be found in the Pharmacy Binder, current package insert, and in Section 6.1.2, below.

[figure not shown]

Figure 4. Drug Administration Schema for Experimental Arm: APR-246 and Azacitidine

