6.2 Criteria for Treatment, Retreatment and Dose Modifications

6.2.1 APR-246

This section outlines the requirements for proceeding with treatment with APR-246, and the protocol rules for APR-246 dose modification due to toxicity.

The

Table **4** describes the routine ECG requirements from screening through Cycle 4 for patients in Experimental Arm:

Table 4. ECG Requirements in Experimental Arm

Time Point	ECG, n	Timing
Baseline/Screening	Triplicate	Within 28 days of Cycle 1 Day 1
Cycle 1, Days 1-4	Triplicate	Pre-dose; Post dose (6 hrs. after start of infusion; ± 30 min)
Cycles 2+, Day 1	Triplicate	Pre-dose

At screening (baseline), 12-lead ECGs should be collected in triplicate to confirm QT interval does not exceed 470 msec. QT interval must be calculated from a mean of all three ECG readings using Fridericia's correction ($QTcF = QT/RR^{0.33}$).

During Cycle 1 ECG should be collected in triplicate prior to infusion of APR-246 and at the end of infusion of APR-246 (6 hours after start of infusion, ± 30 min) on Days 1 - 4. QTcF must be calculated from a mean of all three ECG readings to confirm it does not exceed 470 msec.

If a pre-dose ECG shows $QTcF \geq 470$ msec, the QTc reading should be confirmed by manual assessment using Fridericia's correction ($QTcF = QT/RR^{0.33}$). Serum concentrations of electrolytes should be monitored and corrected, if necessary. Additionally, concomitant medication should be reviewed and adjusted, if necessary. ECG may be repeated at any time, including the same day. APR-246 may only be administered when QTcF has returned to < 470 msec. If APR-246 is given on the same day, procedures outlined in the Schedule of Study Evaluations (Table 8) must be followed. If APR-246 cannot be administered on the same day, that dose must be omitted from the cycle.

If there is a significant change in QTcF, defined as either: a) increase > 60 msec from baseline (or pre-dose), or b) increase to an absolute value ≥ 501 msec, i.e. consistent with NCI CTCAE Grade 3 QTc prolongation, QTc prolongation must be confirmed by a manual assessment of the ECG, and using Fridericia's correction ($QTcF = QT/RR^{0.33}$). If confirmed, the therapy should be interrupted until a cause (electrolyte disorders or an effect of a concomitant medication) has been identified and addressed, and QTcF has returned to < 470 msec. If all other causes for clinically significant QT interval prolongation are excluded, APR-246 must be permanently discontinued.

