6.2.5 Azacitidine Dose Adjustments

Azacitidine dose modifications will follow the Prescribing Information^{30,31} or institutional practice, supported by international recommendations. Azacitidine should be administered SC or IV over 7 consecutive days, Days **4-10**, every 28 days. A single missed dose (for any reason but toxicity) may, at the Investigator's decision, be compensated by adding an additional dosing day for azacitidine (e.g. Day **11**) so that the patient receives the total 7 days of treatment per cycle. If the azacitidine dose interruption is > 2 days, discuss with the Medical Monitor.

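### The synopsis permits a make-up azacitidine dose whatever the reason for the miss and cites Section 6.2.1; Section 6.2.5, where the rule sits, leaves out doses missed for toxicity

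*Combined protocol and SAP*

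**What the plan says.** The make-up rule for azacitidine appears in two places.

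- **Synopsis, row on dose delay and modifications.** It opens with "Dose delays/modifications are permitted per protocol" and continues "A single missed dose may be compensated by adding an additional dosing day for azacitidine". The stated purpose is that the patient "receives the total 7 days of treatment per cycle (see Section 6.2.1"). No reason for the miss is ruled in or out, and the investigator's decision is not mentioned.
- **Section 6.2.5 (Azacitidine Dose Adjustments).** "A single missed dose (for any reason but toxicity) may" be made up by an extra dosing day, at the investigator's decision. Day 11 is given as an example. Interruptions of more than 2 days are to be discussed with the Medical Monitor. The section opens: "Azacitidine dose modifications will follow the Prescribing Information", with institutional practice as an alternative.

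Section 6.2.1, which the synopsis cites, is titled APR-246 and describes its own scope: "This section outlines the requirements for proceeding with treatment with APR-246, and the protocol rules for APR-246 dose modification due to toxicity".

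**The concern.** The same allowance is written once without a condition on the reason and once with one, and the condition missing from the synopsis concerns toxicity. The reference that should lead the reader to the full rule leads to the section on the other drug. Two sites could each act within a text of the same protocol and handle the same event differently: one gives an extra azacitidine day after a dose missed for toxicity, the other does not.

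At stake is consistent dosing of the drug common to both arms. The trial measures the effect of adding APR-246 to azacitidine, so azacitidine should be given under one rule throughout. Dose adjustments and holds are also listed among the safety endpoints in the synopsis, so inconsistent handling would show up in reported data.

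**Working it through.** The plan states no figure on this point, so the check is mainly a comparison of texts.

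**Step 1. Compare the two rules by reason for the miss.**

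| Single azacitidine dose missed because of | Synopsis | Section 6.2.5 |
|---|---|---|
| a reason other than toxicity | make-up day permitted | make-up day permitted, at the investigator's decision |
| toxicity | make-up day permitted (no limit on reason) | outside the permission |

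The texts part only in the toxicity row, apart from the investigator's decision, which the synopsis omits. Both are permissive: each says that a make-up day may be given, and neither says that it must be.

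**Step 2. Follow the synopsis reference.** Section 6.2.1, including Tables 4 to 6, sets ECG requirements, APR-246 dose levels and APR-246 modifications by toxicity grade. Its provisions on omitted or interrupted doses concern APR-246. Azacitidine does come up: after 4 cycles, responding patients may have both drugs delayed by up to 14 days for count recovery. That is a rule on cycle timing and says nothing about replacing a missed daily dose. The reference therefore does not supply the toxicity condition, and it is wrong for the sentence it is attached to.

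**Step 3. Look for a provision that settles the difference.** The opening sentence of Section 6.2.5 defers to the Prescribing Information or institutional practice for azacitidine modifications in general. The same paragraph nevertheless sets a specific make-up rule, and that is the rule stated in two forms. Nothing else in the protocol says which form governs.

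**Step 4. Size in an affected cycle.** The inputs are the daily dose of 75 mg/m² and 7 dosing days per cycle (Sections 6.1.1 and 6.1.2).

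- Planned dose per cycle: 7 × 75 = 525 mg/m².
- One dose as a share: 75 / 525 = 1/7 = 14.3%.

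This applies only to a cycle in which one dose was missed for toxicity and the choice of text decides whether it is made up. The documents give no rate for such cycles, so no trial-level figure can be derived.

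**The case against.** The strongest defence is that a synopsis is a summary. This row begins by deferring to the protocol, and the body has a clearly titled section on azacitidine adjustments that is listed in the table of contents. A site adjusting azacitidine would probably open it. A site that does not make up a dose missed for toxicity complies with both texts. Section 6.2.5 also lets azacitidine modifications follow the label or institutional practice, so some variation between sites exists whatever the synopsis says.

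Much of this stands, and it limits the point. Three stronger readings that a reader might infer are not supported:

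- *That the two texts give opposite instructions.* Both are permissive. The difference is between permitted and excluded.
- *That a site using the synopsis would never meet the toxicity exclusion.* The deferral to the protocol and the title of Section 6.2.5 make that too strong. The wrong reference makes the exclusion easier to miss, but does not hide it.
- *That the conflict changes azacitidine exposure in the experimental arm only.* Section 6.1.1 says that on Day 4 "azacitidine is administered immediately after the APR-246 infusion", which invites the thought that toxicity during the infusion would cost that arm its Day 4 dose. The sentence fixes a sequence only. Section 6.2.2 ends the APR-246 infusion for the day if an event lasts longer than 2 hours and does not mention azacitidine. Table 6 gives modifications for APR-246. Azacitidine toxicity can lead to missed doses in either arm, and the make-up wording is the same for both.

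The defence does not remove the core. The condition is absent from one statement of the rule, and the reference attached to that statement leads to a section without it.

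**Conclusion.** The point holds as an inconsistency in current text together with a wrong cross-reference. For one azacitidine dose missed because of toxicity, the synopsis permits a make-up day that Section 6.2.5 excludes; neither requires it. The synopsis also omits the investigator's decision.

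The effect is at most one seventh of the planned azacitidine dose in an affected cycle. The number of such cycles, and any difference between arms, cannot be obtained from the documents. No effect on the CR comparison is shown.

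The conclusion rests on two readings: that the unqualified synopsis sentence covers every reason for a miss, and that the parenthesis in Section 6.2.5 is meant as a restriction. Both are the ordinary sense of the words. The correction is worth making because the dropped condition concerns toxicity and restoring consistency costs almost nothing.

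**What to change.** Reconcile the synopsis row with Section 6.2.5 so that both state one make-up rule, with the same position on doses missed for toxicity and on the investigator's decision. Change the synopsis reference from Section 6.2.1 to Section 6.2.5. Which rule is clinically right is for the sponsor and its clinical advisers; this review takes no view.

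The cost is about two lines of protocol wording and a notice to sites.

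As an optional addition, the case report form could record the reason for each missed azacitidine dose and whether it was made up, so that azacitidine dose intensity can be compared by arm. The plan already lists dose adjustments and holds as safety endpoints and summarises exposure in the safety population, so this would extend existing provisions. The correction does not depend on it.
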